[figure not shown]
[figure not shown]
[figure not shown]

Clinical Trial Protocol

Document Number:		c15875404-04
EudraCT No.: EU Trial No.:	2017-004231-37	
BI Trial No.:	1368-0013	
BI Investigational Product(s):	Spesolimab (BI 655130)	
Title:	Effisayil™ 1: Multi-center, double-blind, randomized, placebo-controlled, Phase II study to evaluate efficacy, safety and tolerability of a single intravenous dose of BI 655130 in patients with Generalized Pustular Psoriasis (GPP) presenting with an acute flare of moderate to severe intensity	
Lay Title:	A study to test BI 655130 in patients with a flare-up of a skin disease called Generalized Pustular Psoriasis	
Clinical Phase:	II	
Clinical Trial Leader:	

 Phone: [REDACTED]	
Coordinating Investigator:	

 Phone: [REDACTED] Fax: [REDACTED]	
Status:	Final Protocol (Revised Protocol (based on Global Amendment 2)	
Version and Date:	Version: 3.0	Date: 26 Jun 2020
Page 1 of 149		
Proprietary confidential information. © 2020 Boehringer Ingelheim International GmbH or one or more of its affiliated companies. All rights reserved. This document may not - in full or in part - be passed on, reproduced, published or otherwise used without prior written permission.		

CLINICAL TRIAL PROTOCOL SYNOPSIS

Company name	Boehringer Ingelheim
Finished product name	N/A
Active ingredient name:	Spesolimab (BI 655130)
Protocol date	27 June 2018
Revision date	26 Jun 2020
Trial number	1368-0013
Title of trial:	Effisayil™ 1: Multi-center, double-blind, randomized, placebo-controlled, Phase II study to evaluate efficacy, safety and tolerability of a single intravenous dose of BI 655130 in patients with Generalized Pustular Psoriasis (GPP) presenting with an acute flare of moderate to severe intensity
Coordinating Investigator:	 Phone:  ; FAX: 
Trial site(s):	Multi-center trial conducted in 11 to 20 countries.
Clinical phase:	II
Objective(s):	To evaluate efficacy, tolerability and safety of BI 655130 compared to placebo in patients with Generalized Pustular Psoriasis (GPP) presenting with an acute flare of moderate to severe intensity.
Methodology:	Multi-center, placebo-controlled, randomized, double blind
Number of patients entered:	51 patients
Number of patients on each treatment:	34 patients on BI 655130 and 17 patients on placebo
Diagnosis:	Patients with Generalized Pustular Psoriasis (GPP) presenting with an acute flare of moderate to severe intensity.
Main in- and exclusion criteria	Main inclusion criteria: Patients will be enrolled (screened) into the trial, if they meet the following criteria: 
• 1a) Patients with GPPGA of 0 or 1 and a known and documented history of GPP per European Rare And Severe Psoriasis Expert Network (ERASPEN) criteria regardless of IL36RN mutation status,

Proprietary confidential information © 2020 Boehringer Ingelheim International GmbH or one or more of its affiliated companies

with previous evidence of fever, and/or asthenia, and/or myalgia, and/or elevated C-reactive protein, and/or leucocytosis with peripheral blood neutrophilia (above ULN).

OR

- 1b) Patients with an acute flare of moderate to severe intensity meeting the (ERASPEN) criteria of GPP with a known and documented history of GPP (per ERASPEN criteria) regardless of IL36RN mutation status, with previous evidence of fever, and/or asthenia, and/or myalgia, and/or elevated C-reactive protein, and/or leucocytosis with peripheral blood neutrophilia (above ULN).

OR

- 1c) Patients with first episode of an acute GPP flare of moderate to severe intensity with evidence of fever, and/or asthenia, and/or myalgia, and/or elevated C-reactive protein, and/or leucocytosis with peripheral blood neutrophilia (above ULN). For these patients the diagnosis will be confirmed retrospectively by a central external expert/committee.
- Patients may or may not be receiving background treatment with retinoids and/or methotrexate and/or cyclosporine. Patients must discontinue retinoids/methotrexate/cyclosporine prior to receiving the first dose of BI 655130/ placebo.
- Male or female patients, aged 18 to 75 years at screening.
- Signed and dated written informed consent prior to admission to the study in accordance with ICH-GCP and local legislation prior to start of any screening procedures.
- Women of childbearing potential must be ready and able to use highly effective methods of birth control per ICH M3 (R2) that result in a low failure rate of less than 1% per year when used consistently and correctly. Note: A woman is considered of childbearing potential, i.e. fertile, following menarche and until becoming postmenopausal unless permanently sterile. Permanent sterilisation methods include hysterectomy, bilateral salpingectomy and bilateral oophorectomy. Tubal ligation is not a method of permanent sterilization. A postmenopausal state is defined as no menses for 12 months without an alternative medical cause.\

Main Exclusion Criteria:

- Patients with SAPHO (Synovitis–acne–pustulosis–hyperostosis–osteitis) syndrome.
- Patients with primary erythrodermic psoriasis vulgaris.
- Patients with primary plaque psoriasis vulgaris without presence of pustules or with pustules that are restricted to psoriatic plaques.

Clinical Trial Protocol

Page 4 of 149

Proprietary confidential information © 2020 Boehringer Ingelheim International GmbH or one or more of its affiliated companies

	
• Drug-triggered Acute Generalized Exanthematous Pustulosis (AGEP).• Immediate life-threatening flare of GPP or requiring intensive care treatment, according to the investigator's judgement. Life-threatening complications mainly include, but are not limited to, cardiovascular/cytokine driven shock, pulmonary distress syndrome, or renal failure.• Severe, progressive, or uncontrolled hepatic disease, defined as >3-fold Upper Limit of Normal (ULN) elevation in AST or ALT or alkaline phosphatase, or >2-fold ULN elevation in total bilirubin.• Patients with dose escalation of their maintenance therapy with cyclosporine and/or methotrexate and/or retinoids within the 2 weeks prior to receiving the first dose of BI 655130/ placebo.• The initiation of systemic agents such as cyclosporine and/or retinoids and/or methotrexate 2 weeks prior to receiving the first dose of BI 655130/ placebo.
	
Treatment (Visit 2) will be initiated immediately in patients:
 
• Who meet the inclusion criteria above• Who are presenting with an acute GPP flare of moderate to severe intensity, defined by emergence of:
a) Generalized Pustular Psoriasis Physician Global Assessment (GPPGA) score of at least 3 (moderate), andb) presence of fresh pustules (new appearance or worsening of pustules), andc) GPPGA pustulation sub score of at least 2 (mild), andd) at least 5% of Body Surface Area (BSA) covered with erythema and the presence of pustules• And who do not meet any of the exclusion criteria above.
Test product(s):	BI 655130 solution for infusion 60 mg/ml
dose:	900 mg, single dose
mode of administration:	i.v.
Comparator products:	Placebo comparator
dose:	Not applicable
mode of administration:	i.v.
Duration of treatment:	Single dose
Endpoints	Primary Endpoint:

Proprietary confidential information © 2020 Boehringer Ingelheim International GmbH or one or more of its affiliated companies

	
The primary endpoint of the study is:
 
• A Generalized Pustular Psoriasis Physician Global Assessment (GPPGA) pustulation subscore of 0 indicating no visible pustules at Week 1. 
Key Secondary Endpoint:
 
The Key secondary endpoint of the study is:
 
• A GPPGA score of 0 or 1 at Week 1. 
Secondary Endpoints:
 
Secondary Endpoints of the study at Week 4 which are included in the statistical testing strategy in a hierarchical manner subsequent to performance of the tests on the primary endpoint and key secondary endpoint are:
 
• A Psoriasis Area and Severity Index for Generalized Pustular Psoriasis (GPPASI) 75 at Week 4.• Change from baseline in Pain Visual Analog Scale (VAS) score at Week 4.• Change from baseline in Psoriasis Symptom Scale (PSS) score at Week 4.• Change from baseline in Functional Assessment of Chronic Illness Therapy (FACIT) Fatigue score at Week 4. 
Secondary endpoints of the study which are not included in the statistical testing hierarchy are:
 
• A GPPGA 0 or 1 at Week 4.• A GPPGA pustulation subscore of 0 indicating no visible pustules at Week 4.• A GPPASI 50 at Week 1.• A GPPASI 50 at Week 4.• The percent reduction in GPPASI from baseline at Week 1.• The percent reduction in GPPASI from baseline at Week 4.
--	---

Proprietary confidential information © 2020 Boehringer Ingelheim International GmbH or one or more of its affiliated companies

[figure not shown]
	
The following safety endpoint is also defined:
 
• The occurrence of Treatment Emergent Adverse Events (TEAEs).
Safety criteria:	
AEs and Serious Adverse Events (SAEs), AEs of Special Interest, intensity of AEs per the Rheumatology Common Toxicity Criteria (RCTC) version 2.0, safety laboratory tests, 12-lead electrocardiogram (ECG), vital signs (blood pressure [BP], pulse rate [PR], body temperature, body weight), physical examination, infusion site reactions, [REDACTED]

Statistical methods:	
The trial is designed to demonstrate superiority of BI 655130 in the primary endpoint, achievement of pustule clearance at week 1, and the key secondary endpoint, GPPGA (0, 1) at Week 1, relative to placebo. The primary analysis, on each of the primary and key secondary endpoints, will use a Suissa-Shuster test (pooled method) to compare the proportion of patients who achieve a response on BI 655130 versus placebo at week 1.
 
A further hypothesis on the secondary endpoints, GPPASI 75 at Week 4, Pain VAS score at Week 4, PSS score at Week 4 and FACIT Fatigue Score at Week 4, will be tested in a hierarchical manner if the test of the null hypotheses for both primary and key secondary endpoints has previously been rejected.
 
All safety data in this study will be descriptively summarized.

Clinical Trial Protocol

Proprietary confidential information © 2020 Boehringer Ingelheim International GmbH or one or more of its affiliated companies

FLOW CHART

Trial Period	Screening	Treatment	Follow-up Period ^{3,21}													
			V3	V4	V5	V6	V7	V8	V9	V10 ³	V11 ³	V12 ³	V13 ³	V14/ EoS ^{2,3,24}	V15/ EoS ^{2,25}	V16/ EoS ^{2,26}
Visit	V1 ¹	V2 ¹														
Week*					1					2	3	4	8	12	13-18	16-28
Day	-6 months to day -1	1**	2	3	4 ⁵	5 ⁵	6 ⁵	7 ⁵	8	15	22	29	57	85	92-127	113-197
Window										±3d	±3d	±3d	±7d	±7d	±7d	±7d
Informed consent	X ⁶	X ⁶														
Infection testing	X ⁷														X ⁷	
IL36RN mutation status ⁹	X															
Demographics	X															
Medical history	X															
Smoking history	X															
Physical examination ⁴	X ^C	X ^{C,T,8}	X ^T	X ^T	X ^T	X ^T	X ^T	X ^T	X ^{C,T}	X ^T	X ^T					
Vital signs ^{10a,10b}	X	X	X	X	X	X	X	X	X	X	X	X	X	X	X	X
Fever Assessment ¹¹	X	X	X	X	X	X	X	X	X	X	X	X	X	X	X	X
Pregnancy test ¹²	X ^S	X ^{U,(S),8}							X ^{U,(S)}	X ^{U,(S)}	X ^{U,(S)}					
12 lead-ECG ¹³	X	X ⁸							X	X	X	X	X	X	X	X
Safety laboratory tests ¹⁴	X	X ^{14,8}	X	X	X	X	X	X	X ¹⁴	X ¹⁴	X					
Review of in-/exclusion criteria	X	X														

GPPGA		X	X	X	X	X	X	X	X	X	X	X	X	X	X
GPPASI		X	X	X	X	X	X	X	X	X	X	X	X	X	X

Clinical Trial Protocol

Proprietary confidential information © 2020 Boehringer Ingelheim International GmbH or one or more of its affiliated companies

FLOW CHART (CONT'D.)

Trial Period	Screening	Treatment	Follow-up Period ^{3,21}													
Visit	V1 ¹	V2 ¹	V3	V4	V5	V6	V7	V8	V9	V10 ³	V11 ³	V12 ³	V13 ³	V14/ EOS ^{2,3,24}	V15/ EOS ^{2,25}	V16/ EOS ^{2,26}
Week*			1							2	3	4	8	12	13-18	16-28
Day	-6 months to day -1	1**	2	3	4 ⁵	5 ⁵	6 ⁵	7 ⁵	8	15	22	29	57	85	92-127	113-197
Window										±3d	±3d	±3d	±7d	±7d	±7d	±7d
PSS, [REDACTED] ¹⁹		X	X	X	X	X	X	X	X	X	X	X	X	X	X	X
[REDACTED] Pain VAS, FACIT-fatigue ¹⁹		X							X	X	X	X	X	X	X	X
IRT call	X	X							X	X	X	X	X	X	X	X
Dispense/administration study drug ^{3,21}		X							X ²²							
Local tolerability ²⁰ – post dose		X							X ²²							
[REDACTED]		X	X	X	X	X	X	X	X	X	X	X	X			
Adverse events	X	X	X	X	X	X	X	X	X	X	X	X	X	X ²⁹	X ²⁹	X
Concomitant therapy	X	X	X	X	X	X	X	X	X	X	X	X	X	X	X	X
Study Completion														X	X	X
Open Label Extension Trial														X ²³		

ADA, anti-drug antibody; C, complete physical examination; [REDACTED] d, Day; [REDACTED] ECG, Electrocardiogram; EoS, end of study; FACIT-fatigue, Functional Assessment of Chronic Illness Therapy - Fatigue; Fup, Follow-up; GPPASI, Generalized Pustular Psoriasis Area and Severity Index; GPPGA, Generalized Pustular Psoriasis Physician Global Assessment; [REDACTED]; IHC, Immunohistocompatibility Complex; IRT, Interactive Response Technology; [REDACTED] Nab, neutralizing Antibodies; PK, pharmacokinetic; PRO, Patient Reported Outcome; PSS, Psoriatic Symptom Scale; RNASeq, RNA Sequencing; S, serum; T, Targeted physical examination; U, urine; V, Visit; VAS, Visual Analog Scale; Wk, week.

*Week in the flow chart represents the end of each week (e.g. End of Wk1=D8, End of Wk2 =D15, End of Wk3 = D22, End of Wk4 =D29 etc.).

**The day of first study drug administration = Day 1. All subsequent study Days are counted from this Day 1.

¹Visit 1 and Visit 2 can be on the same day if required (see also footnote 8). Initiation of randomized treatment at Visit 2 can only begin if the patient meets the criteria for Initiation of Treatment (see [Section 3.3.4](#)).

²Should a patient prematurely discontinue from the treatment, every effort should be made to keep the patient in the trial and complete all of the remaining study visits. If this is not possible, assessments at V9 (Wk1), V12 (Wk4), and EoS (V14 or V15 or V16 as applicable) should be completed or at a minimum an early EoS visit.

³If a patient qualifies for rescue treatment with open label BI 655130 at either a scheduled or unscheduled visit from after Day 8 and up to and including Week 12, all procedures/measurements listed for V9 (with the exception of skin biopsy, Whole Blood for RNA sequencing, Soluble Protein Biomarkers in Serum and Whole Blood for Flow Cytometry) are to be performed prior to dosing and an IRT call is to be placed prior to dosing.

⁴ C = Complete Physical Examination; T = Targeted physical examination. Refer to [Section 5.2.1](#) for additional details.

Clinical Trial Protocol

Proprietary confidential information © 2020 Boehringer Ingelheim International GmbH or one or more of its affiliated companies

⁵Per physician's assessment, Days 4 through 7 are optional if the patient has achieved complete pustular clearance (GPPGA pustulation sub score = 0) at the prior visit.

⁶Informed consent will be signed at the screening visit (V1). For patients completing V1 and V2 > 6 weeks apart, it is recommended that the patient is asked to re-confirm (verbally) his/her consent to participate in the trial at Visit 2.

⁷Infection testing includes tuberculosis, hepatitis B, hepatitis C, and HIV assessments (see [Table 5.2.3: 1](#)). EoS infection testing should only be done once at V14 or V15 or V16 as applicable.

⁸These procedures do not need to be repeated/Performed when V1 and V2 are performed on the same day.

⁹IL36RN mutation status is to be obtained from the patient's historical data if available.

¹⁰Vital signs: a) On non-study-drug administration days, vital sign assessments are to be done prior to blood sampling; b) On study drug administration days, vital signs will be assessed at pre-dose, at approximately 5 minutes after the end of infusion, and 120 mins after the end of infusion.

¹¹Fever assessments will be recorded on dosing days at three time points. If the patient will receive medication for fever treatment, the fever assessment will be performed prior to taking the anti-fever treatment. These fever assessments must be taken whether or not the patient has an elevated temperature and whether or not the patient takes anti-fever treatment. The fever assessments times are to be separated by intervals of 2 to 4 hours on dosing days. At all other visits (non-dosing days), fever will be assessed once a day and will be completed prior to receiving medication for fever treatment, if anti-fever treatment is given.

¹²Only applicable for women of childbearing potential. S – serum pregnancy test (performed at screening). U – urine pregnancy tests will be performed on-site and only at study drug administration visits. Urine pregnancy testing should be done prior to study drug administration. Study drug should only be administered in case of a negative test result. In case of a positive urine pregnancy test, a serum pregnancy (S) test will be done.

¹³ECG measurements should always precede blood sampling and drug administration (including visits for rescue treatment).

¹⁴Safety laboratory tests include clinical chemistry, haematology, coagulation, and urinalysis, and will be performed centrally. Local Labs are to be used for dosing decisions prior to i.v. administration. Please refer to [Section 5.2.3](#) for further details.

¹⁹These measurements are to be completed by the patient on his/her own, without any help from or interpretation by other people. If the patient is too sick to complete the questionnaires him/herself but is able to reply verbally, a member of the study team should read the instructions, questions, and response options aloud to the patient and collect the patient's verbal response in as neutral and unbiased a manner as possible. If this is not possible either, the questionnaires are not to be completed. The order of completion for PROs is recommended to be as follows: PSS; [REDACTED] pain VAS; FACIT-Fatigue; [REDACTED]

²⁰Local tolerability will be assessed during the study drug administration and for approximately 2 hours after the study drug administration.

²¹After Wk1/D8 and through the follow-up period, should a patient who previously achieved a clinical response (GPPGA 0 or 1) to initial treatment (either BI655130 or placebo or escape medication) experience a recurrence of a GPP flare (see [Table 3.1:1](#)), treatment with a single i.v. dose of 900 mg BI 655130 is to be administered. After D8, only one rescue dose with BI 655130 is permitted if a patient experiences a recurrence of a GPP flare. Subsequent flares are to be treated with escape treatment (SoC) per physician's discretion.

²²Only applicable to patients who meet the qualification for treatment with Open Label (OL) single i.v. dose of 900 mg BI 655130 at Wk1/D8 (see Table 3.1:1)

²³Patients who achieved a clinical improvement to study treatment (not including escape treatment) and show no flare symptoms of moderate/severe intensity at V14 or V15 will be offered to enter into an open label extension (OLE) trial (1368-0025), if they have completed this study (EoS/V14 or V15) and meet the inclusion criteria for the OLE trial.

[figure not shown]
²⁴Patients who receive rescue treatment with OL BI 655130 between Wk7-Wk12 will not have V14. See also footnote 25.

²⁵Only for patients who receive rescue treatment with OL BI 655130 between Wk7 – Wk12. V15 is to be conducted 6 weeks (+/-7days) after rescue treatment with OL BI655130 and includes a response evaluation. If at V15, the patient qualifies to enter OLE trial, then V15 will be considered as EoS. If not, then the patient will have an additional 10 weeks follow-up and have an EoS at V16.

Clinical Trial Protocol

[figure not shown]
Proprietary confidential information © 2020 Boehringer Ingelheim International GmbH or one or more of its affiliated companies

²⁶Only for patients who do not qualify to enter into the OLE trial. V16 is to be conducted 16 weeks (+/-7days) after the last dose of trial medication (excluding the Escape treatment).

If the date of EOS visit for this trial is not the same as the date of first dose of trial medication on the OLE trial (1368-0025), the investigator must continue to capture the AEs in this trial until the patient receives 1st dose in the OLE trial. Please refer to section [5.2.6.2](#) for further details.

TABLE OF CONTENTS

TITLE PAGE	1
CLINICAL TRIAL PROTOCOL SYNOPSIS	2
FLOW CHART	7
TABLE OF CONTENTS	11
LIST OF TABLES	15
LIST OF FIGURES	16
ABBREVIATIONS	17
1. INTRODUCTION.....	19
1.1 MEDICAL BACKGROUND	19
1.2 DRUG PROFILE	21
1.2.1 Mode of action	21

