In a multiple rising dose trial, BI 655130 or placebo have been administered to healthy volunteers at multiple ascending i.v. doses of 3, 6, 10 and 20 mg/kg given weekly for 4 weeks (i.e. 4 administrations) or a single dose of 20mg/kg (8 subjects each, 3:1 on active or PBO). Overall, multiple i.v. doses of 3 mg/kg, 6 mg/kg, and 10 mg/kg, as well as single and multiple doses of 20 mg/kg BI 655130 were found to be safe and well tolerated by the healthy male subjects in this trial. The incidence and intensity of drug related AEs appeared to be higher in the 20 mg/kg multiple dose BI 655130 treatment group than in the other treatment groups, mainly driven by headache. No dose-dependent AEs or other clinically relevant changes in safety laboratory tests, vital signs, or ECG were observed. For further details refer to the current Investigator's Brochure (IB; [c03320877](#)).

The open-label, single group phase I study trial (1368.11) was conducted to investigate the safety, tolerability, pharmacokinetics, pharmacogenomics, and efficacy of a single intravenous dose of BI 655130 (10 mg/kg) in 7 patients with acute flare of generalized pustular psoriasis. The proof-of-concept (PoC) for IL36R inhibition in GPP was achieved in these patients who showed rapid clinical responses to single administrations of BI 655130. Five of these 7 patients became clear or almost clear of GPP 1 week after the infusion, and all of them reached this status 4 weeks after treatment. Within 48 hours of treatment, pustules were completely cleared in 3 patients; pustules were cleared by Week 1 in 5 patients, and by Week 2 in 6 patients. The early response in the skin was also accompanied by an early response in systemic components (C-Reactive Protein [CRP] approaching normalization within 4 weeks). A major improvement in GPPASI was observed in all patients very early with a mean (SD) percent change from baseline of 73.2% (16.2) at Week 2; by

Week 4, this was further reduced to 82.0%, and was maintained to Week 20 (83.6%). Additional improvements (mean [SD]) from baseline to Week 2 were observed in FACIT-F, 12.3 (10.1); Pain-VAS, -45.9 (32.3); and PSS, -5.14 (3.18), all of which were also sustained through Week 4. For further details and most recent results refer to the current IB ([c03320877](#)) and published article in the New England Journal of Medicine ([P19-01888](#)).

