3. DESCRIPTION OF DESIGN AND TRIAL POPULATION

3.1 OVERALL TRIAL DESIGN AND PLAN

This is a multicenter, randomized, double-blind, placebo-controlled Phase II study with one dose of BI 655130/placebo in patients with GPP presenting with an acute flare of moderate to severe intensity. The primary objectives of this trial are to assess the efficacy, safety and tolerability of a single intravenous (i.v.) dose of BI 655130 in comparison to placebo in patients with generalized pustular psoriasis (GPP) presenting with an acute flare of moderate to severe intensity.

Approximately 11 to 20 countries will participate by using sites/centers experienced in the management of GPP.

Fifty-one patients with generalized pustular psoriasis (GPP) presenting with an acute flare of moderate to severe intensity are required to be randomized to receive BI 655130/ placebo (2:1) into this trial.

Patients are considered enrolled (screened) in the study once they have signed the informed consent.

Patients eligible to receive treatment after screening will be able to participate in this study and will be randomized at a ratio of 2:1(BI 655130/Placebo) to one of two treatment groups as shown in [Figure 3.1: 1](#). All patients will receive the first dose of study medication (900 mg i.v. BI 655130 or Placebo) on Day 1 of Week 1 (Randomization). Based on the subsequent treatment response patients will then be followed for 12 to 28 weeks (see [Flow Chart](#)). Study Week in the flow chart represents the end of each week (e.g. End of Wk1=D8, End of Wk2 =D15, End of Wk3 = D22, End of Wk4 =D29 etc.).

During Week 1, D1, D2, D3 and D8 are mandatory visits, however, D4 – D7 are optional visits and need not be attended if a patient has already achieved complete pustular clearance (GPPGA pustulation sub score =0) at the previous visit.

At the discretion of the investigator, patients may be hospitalized prior to, during or following first study drug administration. Thereafter, the decision to discharge a patient from the hospital will also be at the discretion of the investigator, based on the evolution of the GPP flare and the patient's health status.

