5. ASSESSMENTS

5.1 ASSESSMENT OF EFFICACY

The primary endpoint, the key secondary endpoint and the secondary endpoints, [REDACTED] are specified in [Sections 2.1.2, 2.1.3, and 2.2.2](#), respectively.

Skin condition will be assessed by using the Generalized Pustular Psoriasis Physician Global Assessment (GPPGA), the Generalized Pustular Psoriasis Area and Severity Index (GPPASI), and the Psoriatic Symptom Scale (PSS), Patients' questionnaires [REDACTED] Functional Assessment of Chronic Illness Therapy - Fatigue scale (FACIT-Fatigue), Pain VAS, [REDACTED] will be used as well.

[REDACTED]

Additional details for these assessments are provided below. Methodological details for the evaluation of the scores/index are described in the ISF.

Generalized Pustular Psoriasis Physician Global Assessment (GPPGA)

GPPGA relies on clinical assessment of the GPP patient's skin presentation. It is a modified PGA, a physician's assessment of psoriatic lesions, which has been adapted to the evaluation of GPP patients ([R15-5200](#)). The investigator (or qualified site personnel) scores the erythema, pustules, and scaling of all GPP lesions from 0 to 4. Each component is graded separately, the average is calculated, and the final GPPGA is determined from this composite score. A lower score indicates a lesser severity, with 0 being clear and 1 being almost clear.

GPPGA is provided in [Appendix 10.1.1](#); this score will be measured at the timepoint noted in the study [Flow Chart](#).

Generalized Pustular Psoriasis Area and Severity Index (GPPASI)

The GPPASI is an adaptation for GPP patients of the PASI, an established measure of severity and area of psoriatic lesions in patients with psoriasis ([R96-3541](#)). Similar adaptions have been used for PPP ([R16-3360](#)). In the GPPASI, the induration component has been substituted with the pustules component. It is a tool that provides a numeric scoring for a patient's overall GPP disease state, ranging from 0 to 72. It is a linear combination of percent of surface area of skin that is affected by erythema, pustules and scaling and the severity of erythema, pustules, and scaling (desquamation) over 4 body regions.

GPPASI is provided in [Appendix 10.1.2](#); this score will be measured at the timepoint noted in the study Flow Chart.

FACIT-Fatigue scale

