7.3.1 Primary endpoint analyses

The analysis for the primary endpoint includes the evaluation of patients achieving a GPPGA pustulation subscore of 0 at Week 1.

Any use of escape medication, e.g. use of restricted medication for disease worsening in [Table 4.2.2.1: 1](#), prior to observing the primary endpoint is considered to reflect a failure to achieve the endpoint outcome, i.e. non-response (see primary endpoint definition in [Section 2.1.2](#)).

Due to the small sample size of the trial, an exact statistical test will be used to assess the statistical significance of the treatment effect versus Placebo. Since the traditional Fisher's exact test may be unnecessarily conservative, an alternative test, the Suissa-Shuster Z-pooled test, will be implemented in this trial. The Suissa-Shuster Z-pooled test always preserves the type I error level and is usually more powerful than the Fisher's exact test.

The primary endpoint will be tested, for the RS, using the Suissa-Shuster Z-pooled test at a 1-sided, alpha level of 0.025.

Secondary analysis of the primary endpoint will include:

- A sensitivity analysis utilizing the PPS;
- Analysis of an additional estimand whereby any use of escape medication prior to week 1 will be considered to represent a non-response. For patients who use other restricted medication but not for disease worsening prior to Week 1, data will be censored for further analysis following the use and imputed using the methods described in [Section 7.5](#).
- Sensitivity analyses which utilize alternative methods for the handling of missing data as described in Section 7.5.
- A subgroup assessment according to the Japan vs. non-Japan strata will be assessed descriptively
- Sensitivity analyses to adjust for the covariates, IL36R mutation status (Yes vs. No) and baseline GPPGA total score (3 vs. 4) respectively using logistic regression.

Further analysis of the primary endpoint will include:

- Analysis of the time to first achievement of a response on the primary endpoint via Kaplan-Meier methods.

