7.3.2 Key Secondary endpoint analyses

The analysis for the key secondary endpoint, for patients achieving a GPPGA score 0 or 1 at Week 1, will be performed in the same manner as described for the analyses of the primary endpoint.

Any use of escape medication, e.g. use of restricted medication for disease worsening in [Table 4.2.2.1: 1](#), prior to observing the key secondary endpoint is considered to reflect a failure to achieve the endpoint outcome, i.e. non-response (see key secondary endpoint definition [Section 2.1.3](#)).

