4. CHANGES IN THE PLANNED ANALYSIS OF THE STUDY

Following further endpoints are added to TSAP:

- Change from baseline in GPPGA total score, by visit
- Change from baseline in GPPGA pustulation subscore, by visit
- GPPGA clear/almost clear (modified) defined as a GPPGA total score of 0 or 1 and with all subscores < 3, by visit
- A GPPGA erythema sub-score of 0 or 1, by visit.
- A GPPGA scaling sub-score of 0 or 1, by visit.
- A GPPGA pustulation sub-score drop by at least 2 points from baseline, by visit.
- A Pain VAS drop by at least 30 points from baseline.
- Percentage change from baseline in each of GPPASI pustulation, erythema and scaling severities.
- [REDACTED]
- A PSS score of 0, by visit
- A FACIT-Fatigue score improvement of at least 4 points, by visit

For time to first achievement of GPPGA pustulation score of 0 or GPPGA score of 0 or 1, the first day should be day of randomized treatment if it is different from randomization. For Wilcoxon testing, the calculations of ranks should be also relative to Day 1.

Percentage change from baseline in GPPASI will be calculated instead of percentage reduction in GPPASI. For example, if there is 50% reduction in GPPASI score, it means % change from baseline in GPPASI is -50%.

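### Visits on Days 4-7 may be skipped once pustules clear even if GPPGA is still 2 or more, so the supportive time-to-GPPGA-0/1 estimate can date some responses 1 to 4 days late, mainly on spesolimab

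*Protocol*

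**What the plan says.** **Visit schedule.** Protocol Section 3.1 fixes the Week 1 grid: "During Week 1, D1, D2, D3 and D8 are mandatory visits". It adds that "D4 – D7 are optional visits and need not be attended if a patient has already achieved complete pustular clearance". Flow Chart footnote 5 gives the same rule and leaves its use to the physician's assessment: "Days 4 through 7 are optional if the patient has achieved complete pustular clearance (GPPGA pustulation sub score = 0) at the prior visit". Neither place mentions the total GPPGA.

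**Score.** Protocol Section 5.1 says of erythema, pustules and scaling: "Each component is graded separately, the average is calculated, and the final GPPGA is determined from this composite score". Under Appendix 10.1.1, a total of 0 or 1 needs a component mean below 1.5.

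**Analysis.** Protocol Section 7.3.1 lists, as a further analysis, "Analysis of the time to first achievement of a response on the primary endpoint via Kaplan-Meier methods". Section 7.3.2 says the key secondary endpoint, GPPGA 0/1 at Week 1, "will be performed in the same manner as described for the analyses of the primary endpoint". SAP Section 4 sets the time origin for both: "For time to first achievement of GPPGA pustulation score of 0 or GPPGA score of 0 or 1", it is the day of randomized treatment.

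**Optional visits in the SAP.** Table 6.7: 1 (footnote B) and the end of Section 6.7 keep Visits 5-8 out of tables and figures unless specified otherwise. The visible SAP does not say how these visits enter a time-to-response analysis.

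**The concern.** The exemption suits time to pustule clearance, because visits can lapse only after that event has been seen. It does not suit time to GPPGA 0/1, because visits can lapse before that event. How closely a patient is observed then depends on how well the patient has already responded. Ordinary Kaplan-Meier dates a response to the visit where it is first seen, so it takes no account of this.

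At stake is a supportive description of onset. Rapid onset is part of the need stated in Protocol Sections 1.1 and 1.3, and Section 1.3 says the results will support first registration. The spesolimab curve for GPPGA 0/1 could run late between Days 4 and 7 and then step up at Day 8 because of the schedule rather than the disease.

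**Working it through.** The documents give no figure for time to GPPGA 0/1. Their nearest figure is the Week 1 power, so that is checked first.

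1. **Week 1 power (Protocol 7.7).** Inputs: 34 versus 17 patients, response 0.6 versus 0.1 on each endpoint, one-sided alpha 0.025, correlation 0.65. The exact Suissa-Shuster Z-pooled test has critical Z 2.048 and size 0.0238. Power is 96.3% for the primary endpoint (stated 96.3%). Simulation of correlated pairs (400,000 runs) gives 93.9% for both endpoints (stated 93.9%). Both are read at the mandatory Day 8 visit, so the exemption changes neither.

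2. **Can GPPGA stay at 2 or more with pustules 0?** The mean is (erythema + 0 + scaling)/3. It is at least 1.5 when erythema + scaling ≥ 4.5, that is, ≥ 5. Of the 25 erythema-scaling pairs, 10 meet this: nine give GPPGA 2 and one gives 3. Example: (3 + 0 + 3)/3 = 2.0, so GPPGA 2. This count shows possibility, not frequency.

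3. **Is that state plausible here?** Protocol 3.3.4 requires GPPGA of at least 3 (mean ≥ 2.5, so component sum ≥ 8) and pustulation of at least 2.
   - Pustulation 2 at entry: erythema + scaling ≥ 6.
   - Pustulation 3 at entry: erythema + scaling ≥ 5.
   - Pustulation 4 at entry: erythema + scaling ≥ 4.

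   With pustulation 2 or 3 at entry, pustule clearance alone cannot give GPPGA 0/1; erythema or scaling must also improve. With pustulation 4, clearance alone is enough only if erythema + scaling is exactly 4.

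4. **Discordance in the planning values.** P(both responses) = 0.6² + 0.65 × 0.6 × 0.4 = 0.36 + 0.156 = 0.516. Among pustule-clear spesolimab patients at Week 1, 1 − 0.516/0.6 = 14% would still have GPPGA above 1. No corresponding Day 3 figure is given.

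5. **Delay for a patient with GPPGA still 2 or more who skips every exempt visit.**

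| Pustules first seen clear | True day of first GPPGA 0/1 | Recorded | Delay (days) |
|---|---|---|---|
| Day 2 or 3 | 4, 5, 6, 7 | Day 8 | 4, 3, 2, 1 |
| Day 4 | 5, 6, 7 | Day 8 | 3, 2, 1 |
| Day 5 | 6, 7 | Day 8 | 2, 1 |
| Day 6 | 7 | Day 8 | 1 |

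   A response on Day 2 or 3 has no delay, because those visits are mandatory. A patient with pustules still present who attends daily also has none.

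6. **Which arm, and how many could be exempt?** Protocol 1.2.3 reports for the proof-of-concept trial (7 patients): "Within 48 hours of treatment, pustules were completely cleared in 3 patients". 3/7 = 43%, exact 95% CI 9.9% to 81.6%. Applied to 34 patients: 0.43 × 34 ≈ 15, range 0.099 × 34 ≈ 3 to 0.816 × 34 ≈ 28. This counts patients who could be exempt from Day 4. Those affected are the subset who still have GPPGA 2 or more at Day 3, skip visits, and first reach 0/1 on Days 4-7. Patients whose pustules clear on Days 4-6 may add to them, with shorter delays. On placebo, the planning rate implies only 0.1 × 17 = 1.7 patients clear even at Week 1.

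**The case against.** The strongest reply is that the analysis text may simply not be visible. SAP Sections 7.4 and 7.5.1 contain no Kaplan-Meier specification. Section 7.6 is absent from the public text, although other sections cross-refer to 7.6.2, 7.6.3 and 7.6.5. A rule for dating responses could be there. This stands, and it makes the fix conditional. The display default for Visits 5-8 does not settle the matter: it says what is shown by visit, not how an event is dated.

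The analysis is also supportive, outside the testing hierarchy, and has no between-arm test in the visible text. Any delay runs against spesolimab, so it cannot create a false claim of fast onset. This stands too and limits the severity.

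Three stronger readings are tempting, but the documents do not support them:

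- **That fast responders are seen only at Day 8.** Days 2 and 3 are mandatory, skipping is permitted rather than required, and hospitalized patients have their visits as inpatients (Protocol 6.2).
- **That about 15 spesolimab patients will be misdated.** That figure estimates possible exemption, from seven patients. In the same trial 5 of 7 had cleared pustules by Week 1, and 5 of 7 were clear or almost clear at that time. The affected group could be very small.
- **That the curve is certainly biased.** That would need data on discordant patients and actual skipping, and the documents give neither.

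**Conclusion.** The mismatch is real and minor. For patients who use the exemption with GPPGA still at 2 or more, a first GPPGA 0/1 on Days 4-7 is recorded 1 to 4 days late. Because early clearance is expected mainly on spesolimab, the supportive Kaplan-Meier estimate may be delayed in that arm.

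The conclusion rests on three assumptions: some patients do skip, some of them reach GPPGA 0/1 between Days 4 and 7, and no unseen SAP text already handles the spacing. The size of the effect on the curve cannot be derived from the documents. The arm imbalance also assumes that the small open-label proof-of-concept trial, which used weight-based dosing, is a fair guide to early clearance here.

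**What to change.** Apply the change wherever the SAP specifies the time-to-GPPGA-0/1 analysis (possibly Section 7.6), unless a rule is already there. Either option is enough:

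- Treat first GPPGA 0/1 as interval-censored between the last attended visit without response and the first visit with response.
- Add a Kaplan-Meier analysis in both arms restricted to the visits mandatory for everyone (Days 2, 3 and 8, then the later scheduled visits), next to the all-visit curve.

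The cost is some SAP wording and one additional analysis. The common grid also gives coarser timing within Week 1, which is why the all-visit curve should stay. No change to the visit schedule, sample size or confirmatory tests is needed.
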